3 STUDY OBJECTIVES AND OUTCOME MEASURES

Primary Objectives

1. To assess the serum anti-HA hemagglutination-inhibition (HAI) response to influenza A/H7N9 antigen (with and without adjuvant) at Day 57 (approximately one month after the second study vaccination with A/H7N9 vaccine ± AS03) and influenza A/H3N2v antigen at Day 29 (approximately one month after the study vaccination with A/H3N2v vaccine).
2. To identify differentially expressed genes in human immune cells on Days 2, 4, and 29 (following the first study vaccination with A/H7N9 vaccine ± AS03) and on Days 30, 32, and 36 (following the second study vaccination with A/H7N9 vaccine ± AS03), compared to baseline assessments performed prior to each study vaccination (Days -7, 1, and 29).

Primary Outcome Measures

1. Percentage of subjects achieving seroconversion (defined as either a pre-vaccination HAI titer <1:10 and a post-vaccination HAI titer ≥1:40 or a pre-vaccination HAI titer ≥1:10 and a minimum four-fold rise in post-vaccination HAI antibody titer) at approximately 28 days after the second study vaccination (A/H7N9 vaccine, with and without adjuvant).
2. Percentage of subjects achieving seroconversion at approximately 28 days after the study vaccination with A/H3N2v vaccine.
3. Number of differentially expressed genes based on RNA expression as determined by RNA-Seq analysis, in human immune cells at Days 2, 4, 29, 30, 32, and 36 after study vaccination with AS03-adjuvanted and unadjuvanted A/H7N9 vaccine, as compared to baseline assessments performed prior to vaccination (Days -7, 1, and 29).

Secondary Objectives

1. To compare plasma cytokine and chemokine profiles at specific time points and between treatment arms:
 - a. Post-vaccination time points [(Days 2 and 4; Day 8 (A/H3N2v arm only)), and Days 30, 32, and 36 (A/H7N9 arms only) with pre-vaccination time points (Days -7 and 1, prior to first study vaccination and Day 29, prior to second study vaccination (A/H7N9 arms only)).

2. To assess the neutralizing antibody responses to influenza A/H7N9 antigen (with and without adjuvant) at Day 57 (approximately one month after the second study vaccination with A/H7N9 vaccine ± AS03) and influenza A/H3N2v antigen at Day 29 (approximately one month after the study vaccination with A/H3N2v vaccine).
3. To identify differentially expressed genes in human immune cells on Days 2, 4, and 8 following one intramuscular dose of influenza A/H3N2v vaccine compared to baseline assessments performed prior to study vaccination (Day -7 and Day 1).

Secondary Outcome Measures

1. Plasma measurement of cytokines and chemokines at each study visit, comparing:
 - a. Post-vaccination time points with pre-vaccination time points by treatment arms.
 - b. AS03-adjuvanted influenza A/H7N9 responses to unadjuvanted influenza A/H7N9 responses.
 - c. Influenza A/H3N2v vaccine to unadjuvanted influenza A/H7N9 vaccine.
 - d. Influenza A/H3N2v vaccine to adjuvanted A/H7N9 vaccine.
2. Serologic response to influenza hemagglutinin:
 - a. Percentage of subjects achieving seroconversion (defined as either a pre-vaccination Neut titer <1:10 and a post-vaccination Neut titer \geq 1:40 or a pre-vaccination Neut titer \geq 1:10 and a minimum four-fold rise in post-vaccination Neut titer) at approximately 28 days after the second study vaccination (A/H7N9 vaccine, with and without adjuvant).
 - b. Percentage of subjects achieving seroconversion at approximately 28 days after the study vaccination with influenza A/H3N2v vaccine.
 - c. Geometric Mean Titers of serum HAI and Neut antibody at baseline (Day -7 and 1) and 28 days after influenza A/H3N2v vaccination.
 - d. Geometric Mean Titers of serum HAI and Neut antibody at baseline (Day -7 and 1), and 28 days after both the first and the second dose of influenza A/H7N9 vaccine (with and without adjuvant).
3. Number of differentially expressed genes based on RNA-Seq analysis in human immune cells at Days 2, 4, and 8 after study vaccination, as compared to baseline assessments (Days -7 and 1) after influenza A/H3N2v vaccine.

Tertiary Objectives

1. To assess the frequency of adverse events.

2. To identify differentially abundant cellular proteins in human immune cells on Days 2, 4, and 8 following one intramuscular dose of influenza A/H3N2v vaccine compared to baseline assessments performed prior to study vaccination (Day -7 and Day 1).
3. To identify differentially abundant cellular proteins in human immune cells on Days 2, 4, and 29 (following first study vaccination with A/H7N9 vaccine ± AS03) and Days 30, 32, and 36 (following second study vaccination with A/H7N9 vaccine ± AS03), compared to baseline assessments performed prior to study vaccination (Days -7, 1, and 29).

Tertiary Outcome Measures

1. Occurrence of solicited local reactogenicity events within 7 days after each study vaccination.
2. Occurrence of solicited systemic reactogenicity events within 7 days after each study vaccination.
3. Occurrence of unsolicited AEs collected for approximately 28 days after last study vaccination.
4. Occurrence of SAEs and MAAEs including new-onset chronic medical conditions and potentially immune-mediated medical conditions for approximately 1 month (A/H3N2v arm) and 12 months (A/H7N9 arms) after last study vaccination.
5. Number of differentially abundant proteins based on protein abundance as determined by quantitative proteomics in human immune cells at Days 2, 4, and 8 after study vaccination, as compared to baseline assessments (Days -7 and 1) after influenza A/H3N2v vaccine.
6. Number of differentially abundant proteins based on protein abundance as determined by quantitative proteomics analysis, in human immune cells at Days 2, 4, 29, 30, 32, and 36 after study vaccination with AS03-adjuvanted and unadjuvanted A/H7N9 vaccine comparing changes in protein abundance between treatment arms (A/H7N9 vaccine vs. A/H7N9 vaccine + AS03).

Exploratory Objectives

1. To identify and characterize differentially expressed genes in human immune cells on Days 2, 4, and 29 (following the first study vaccination with A/H7N9 vaccine \pm AS03) and on Days 30, 32, and 36 (following the second study vaccination with A/H7N9 vaccine \pm AS03) that differ between treatments (A/H7N9 vaccine vs. A/H7N9 vaccine + AS03).
2. To identify and characterize differentially abundant cellular proteins in human immune cells on Days 2, 4, and 29 (following the first study vaccination with A/H7N9 vaccine \pm AS03) and on Days 30, 32, and 36 (following the second study vaccination with A/H7N9 vaccine \pm AS03) that differ between treatments (A/H7N9 vaccine vs. A/H7N9 vaccine + AS03).
3. To identify and characterize differentially expressed genes in human immune cells on Days 2 and 4 (following the first study vaccination) that differ in baseline responses (Days -7, and 1) between treatments (A/H3N2v vaccine vs. A/H7N9 vaccine and A/H3N2v vaccine vs. A/H7N9 vaccine + AS03).
4. To identify and characterize differentially abundant cellular proteins in human immune cells on Days 2 and 4 (following the first study vaccination) that differ in baseline responses (Days -7, and 1) between treatments (A/H3N2v vaccine vs. A/H7N9 vaccine and A/H3N2v vaccine vs. A/H7N9 vaccine + AS03).
5. To identify transcriptomic and proteomic signatures in human immune cells that correlate with influenza seroconversion and with peak HAI titers.
6. To correlate plasma cytokine profiles with transcriptomic and proteomic profiles in subjects receiving influenza A/H3N2v vaccine or influenza A/H7N9 \pm AS03 vaccine.
7. Exploratory inspection of transcriptomics\proteomics response signatures for subjects with unexpected or severe safety profiles that are related to the study products.

Exploratory Outcome Measures

1. RNA expression, clusters of co-expressed genes, enriched pathways, and other functional modules as determined by RNA-Seq analysis, in human immune cells at Days 2, 4, 29, 30, 32, and 36 after study vaccination with AS03-adjuvanted and unadjuvanted A/H7N9 vaccine comparing changes in RNA expression between treatment arms (A/H7N9 vaccine vs. A/H7N9 vaccine + AS03).

2. Protein abundance, clusters of co-abundant proteins, enriched pathways, and other functional modules as determined by quantitative proteomics analysis, in human immune cells at Days 2, 4, 29, 30, 32, and 36 after study vaccination with AS03-adjuvanted and unadjuvanted A/H7N9 vaccine comparing changes in protein abundance between treatment arms (A/H7N9 vaccine vs. A/H7N9 vaccine + AS03).
3. RNA expression, clusters of co-expressed genes, enriched pathways, and other functional modules as determined by RNA-Seq analysis, in human immune cells at Days 2, 4, and 29 after study vaccination comparing baseline changes in RNA expression between treatment arms (A/H3N2v vaccine vs. A/H7N9 vaccine and A/H3N2v vaccine vs. A/H7N9 vaccine + AS03).
4. Protein abundance, clusters of co-abundant proteins, enriched pathways, and other functional modules as determined by quantitative proteomics analysis, in human immune cells at Days 2, 4, and 29 after first study vaccination comparing baseline changes (Days -7, and 1) in protein abundance between treatment arms (A/H3N2v vaccine vs. A/H7N9 vaccine and A/H3N2v vaccine vs. A/H7N9 vaccine + AS03).
5. Changes from baseline (Days -7, 1, and 29) in RNA expression or protein abundance that best correlate with influenza A/H7N9 seroconversion and with peak HAI titers at Days 2 and 4 (following first study vaccination) as well as Days 30, 32, and 36 (following second study vaccination).
6. Changes from baseline (Days -7, 1, and 29) in RNA expression or protein abundance that best correlate with baseline changes in cytokine concentrations at Days 2, 4, 8 (A/H3N2v arm only) and 29 (following first study vaccination) as well as Days 30, 32, and 36 (following second study vaccination).
7. Exploratory summaries of transcriptomics/proteomics response signatures for subjects with unexpected or severe safety profiles.
8. Lists of differential genes and proteins identified as part of the primary and secondary objectives.

4 STUDY DESIGN

This is a single center, randomized, partially-blinded, Phase II, small, targeted, prospective study in approximately 30 healthy male and non-pregnant female subjects aged 18 to 49 years old, inclusive, designed to evaluate and compare the immunogenicity between an intramuscular monovalent inactivated influenza A/H7N9 virus vaccine manufactured by Sanofi Pasteur given with and without AS03 adjuvant manufactured by GlaxoSmithKline, and an intramuscular unadjuvanted monovalent inactivated influenza A/H3N2v virus vaccine manufactured by Sanofi Pasteur.

This study will use a standard and systems biology approach to assess the human early gene and protein signatures expressed at baseline (approximately Days -7 and 1), and at approximately Days 2, 4, and 8 (A/H3N2v-vaccinated subjects only) after the first study vaccination in each treatment arm as well as at approximately Days 29, 30, 32, and 36 in A/H7N9-vaccinated subjects only. Cellular immunogenicity (systems biology studies) data will be integrated with serologic immunogenicity (HAI and Neut antibody assays) and reactogenicity data to develop a systems model of the human immune response to unadjuvanted monovalent inactivated influenza A/H3N2v virus vaccine and monovalent inactivated influenza A/H7N9 virus vaccine given with and without AS03 adjuvant.

This study will use venous blood samples and subject data collected from a total of thirty vaccinated subjects randomly divided into three equal treatment arms. The first treatment arm (n=10) will be vaccinated with one dose of 15 µg of A/H3N2v HA. The second treatment arm (n=10) will be vaccinated with two doses of 3.75 µg of A/H7N9 HA given with AS03 approximately 28 days apart. The third treatment arm (n=10) will be vaccinated with two doses of 3.75 µg of A/H7N9 HA given without AS03 adjuvant approximately 28 days apart. All study vaccinations will be administered intramuscularly.

Reactogenicity will be measured by the occurrence of solicited injection site and systemic reactions from the time of each study vaccination through 8 days after each study vaccination. Unsolicited non-serious adverse events (AEs) will be collected from the time of each study vaccination through approximately 28 days after each study vaccination. Serious adverse events (SAEs) and medically-attended adverse events (MAAEs) including new-onset chronic medical conditions (NOCMCs) and potentially immune-mediated medical conditions (PIMMCs) will be collected from the time of the first study vaccination through approximately 1 month (A/H3N2v arm) and 12 months (A/H7N9 arms) after the last study vaccination.

Venous blood samples (approximately 90 mL) will be collected from subjects at approximately Days -7 and 1 (immediately prior to the first study vaccination), and at approximately Days 2, 4;

and 8 (A/H3N2v-vaccinated subjects only) after the first study vaccination for systems biology studies (cytokine and chemokine levels, immune cell activation status, and whole transcriptome and proteome profiles of the major blood immune cells). Additionally, subjects in either treatment arm receiving A/H7N9 vaccine will have additional blood samples collected at approximately Days 29 (this will be collected immediately prior to the second study vaccination for subjects in either group receiving A/H7N9), 30, 32, and 36 after the first study vaccination for systems biology studies.

Serological assessment (hemagglutination inhibition (HAI) and neutralizing (Neut) antibody assays) will also be conducted on venous blood samples (approximately 10 mL) collected from subjects at Day 1 (immediately prior to the first study vaccination), and at approximately Days 29 (for A/H7N9-vaccinated subjects this will be collected immediately prior to the second study vaccination) and 57 (A/H7N9-vaccinated subjects only) after the first study vaccination.

We will quantify and characterize serum cytokine/chemokine levels, as well as transcriptomic and proteomic profiles from individual immune cell compartments, comparing this with standard serologic assessment to vaccine.

Urine samples (approximately 20 mL) will also be collected from subjects at approximately Days -7, 1, 2, 4, 8 (A/H3N2v-vaccinated subjects only), 29, 30, 32, and 36 for future research.

Note: Days 29, 30, 32, and 36 will apply only to A/H7N9-vaccinated subjects.

5 STUDY ENROLLMENT AND WITHDRAWAL

Approximately 30 healthy male and non-pregnant female subjects aged 18 to 49 years old, inclusive, who meet all eligibility criteria will be enrolled in this study from one participating VTEU site. Enrollment will occur over a 6-month period, and the target population will reflect the community at large. Information regarding this study may be mailed or emailed to potential subjects who have previously participated in vaccine trials conducted at the participating VTEU site. Other forms and/or mechanisms of recruitment may also be used. The local IRB will approve all materials prior to use.

Subject Inclusion and Exclusion Criteria must be assessed by a study clinician licensed to make medical diagnoses and listed on the Form FDA 1572 as the site principal investigator or sub-investigator.

No exemptions are granted on Subject Inclusion or Exclusion Criteria in DMID-sponsored studies. Questions about eligibility should be directed toward the DMID Medical Officer.

5.1 Eligibility Criteria

5.1.1 Subject Inclusion Criteria

Subjects eligible to participate in this study must meet all of the following inclusion criteria:

1. Provide written informed consent prior to initiation of any study procedures.
2. Are able to understand and comply with planned study procedures and be available for all study visits.
3. Are males or non-pregnant females, 18 to 49 years old, inclusive.
4. Are in good health¹.

¹As determined by medical history and targeted physical examination, if indicated based on medical history, to evaluate acute or currently ongoing chronic medical diagnoses or conditions, defined as those that have been present for at least 90 days, that would affect the assessment of the safety of subjects or the immunogenicity of study vaccinations. Chronic medical diagnoses or conditions should be stable for the last 60 days. This includes no change in chronic prescription medication, dose, or frequency as a result of deterioration of the chronic medical diagnosis or condition in the 60 days prior to enrollment. Any prescription change that is due to change of health care provider, insurance company, etc., or that is done for financial reasons, as long as in the same class of medication, will not be considered a deviation of this inclusion criterion. Any change in prescription medication due to **improvement** of a disease outcome, as determined by the site principal investigator or appropriate sub-investigator, will not be considered a deviation of this inclusion criterion. Subjects may be on chronic or as needed (prn) medications if, in the opinion of the site principal investigator or appropriate sub-investigator, they pose no additional risk to subject safety or assessment of reactogenicity and immunogenicity and do not indicate a worsening of medical diagnosis or

condition. Similarly, medication changes subsequent to enrollment and study vaccination are acceptable provided there was no deterioration in the subject's chronic medical condition that necessitated a medication change, and there is no additional risk to the subject or interference with the evaluation of responses to study vaccination. Note: Topical, nasal, and inhaled medications (with the exception of inhaled corticosteroids as outlined in the Subject Exclusion Criteria (see Section 5.1.2)), herbals, vitamins, and supplements are permitted.

5. Oral temperature is less than 100.4°F.
6. Pulse is 50 to 115 bpm, inclusive.
7. Systolic blood pressure is 85 to 150 mm Hg, inclusive.
8. Diastolic blood pressure is 55 to 95 mm Hg, inclusive.
9. Erythrocyte sedimentation rate (ESR) is less than 30 mm per hour.
10. Women of childbearing potential² must use an acceptable contraception method³ from 30 days before first study vaccination until 60 days after last study vaccination.

²*Not sterilized via tubal ligation, bilateral oophorectomy, hysterectomy or successful Essure® placement (permanent, non-surgical, non-hormonal sterilization) with documented radiological confirmation test at least 90 days after the procedure, and still menstruating or <1 year of the last menses if menopausal.*

³*Includes, but is not limited to, non-male sexual relationships, abstinence from sexual intercourse with a male partner, monogamous relationship with vasectomized partner who has been vasectomized for 180 days or more prior to the subject receiving the first study vaccination, barrier methods such as condoms or diaphragms with spermicide or foam, effective intrauterine devices, NuvaRing®, and licensed hormonal methods such as implants, injectables or oral contraceptives ("the pill").*

11. Women of childbearing potential must have a negative urine or serum pregnancy test within 24 hours prior to study vaccination.

5.1.2 Subject Exclusion Criteria

Subjects eligible to participate in this study must not meet any of the following exclusion criteria:

1. Have an acute illness⁴, as determined by the site principal investigator or appropriate sub-investigator, within 72 hours prior to study vaccination.

⁴*An acute illness which is nearly resolved with only minor residual symptoms remaining is allowable if, in the opinion of the site principal investigator or appropriate sub-investigator, the residual symptoms will not interfere with the ability to assess safety parameters as required by the protocol.*

2. Have any medical disease or condition that, in the opinion of the site principal investigator or appropriate sub-investigator, is a contraindication to study participation⁵.

⁵Including acute or chronic medical disease or condition, defined as persisting for at least 90 days that would place the subject at an unacceptable risk of injury, render the subject unable to meet the requirements of the protocol, or may interfere with the evaluation of responses or the subject's successful completion of this study.

3. Have immunosuppression as a result of an underlying illness or treatment, or use of anticancer chemotherapy or radiation therapy (cytotoxic) within 3 years prior to study vaccination.
4. Have known active neoplastic disease (excluding non-melanoma skin cancer) or a history of any hematologic malignancy.
5. Have known human immunodeficiency virus (HIV), hepatitis B, or hepatitis C infection.
6. Have known hypersensitivity or allergy to eggs, egg or chicken protein, squalene-based adjuvants, or other components of the study vaccines.
7. Have a history of severe reactions following previous immunization with licensed or unlicensed influenza virus vaccines.
8. Have a personal or family history of narcolepsy.
9. Have a history of Guillain-Barré syndrome.
10. Have a history of convulsions or encephalomyelitis within 90 days prior to study vaccination.
11. Have a history of a potentially immune-mediated medical condition⁶.

⁶Refer to Appendix A: List of Potentially Immune-Mediated Medical Conditions.

12. Have a history of alcohol or drug abuse within 5 years prior to study vaccination.
13. Have any diagnosis, current or past, of schizophrenia, bipolar disease, or other psychiatric diagnosis that may interfere with subject compliance or safety evaluations.
14. Have been hospitalized for psychiatric illness, history of suicide attempt, or confinement for danger to self or others within 10 years prior to study vaccination.
15. Have taken oral or parenteral (including intra-articular) corticosteroids of any dose within 30 days prior to study vaccination.

-
16. Have taken high-dose inhaled corticosteroids within 30 days prior to study vaccination. High-dose defined as >840 mcg/day of beclomethasone dipropionate CFC or equivalent.
 17. Received licensed live vaccine within 30 days prior to the first study vaccination, or plans to receive licensed live vaccine within 30 days before or after each study vaccination.
 18. Received licensed inactivated vaccine within 14 days prior to the first study vaccination, or plans to receive licensed inactivated vaccine within 14 days before or after each study vaccination.
 19. Received immunoglobulin or other blood products (with exception of Rho D immunoglobulin) within 90 days prior to study vaccination.
 20. Received an experimental agent⁷ within 30 days prior to the first study vaccination, or expects to receive an experimental agent⁸ during the 13-month study-reporting period.
⁷Including vaccine, drug, biologic, device, blood product, or medication.
⁸Other than from participation in this study.
 21. Are participating or plan to participate in another clinical trial with an interventional agent⁹ that will be received during the 13-month study-reporting period.
⁹Including licensed or unlicensed vaccine, drug, biologic, device, blood product, or medication.
 22. Prior participation in a clinical trial of influenza A/H7 vaccine¹⁰ or have a history of influenza A/H7 virus actual or potential exposure or infection prior to the first study vaccination.
¹⁰And assigned to a group receiving influenza A/H7 vaccine, does not apply to documented placebo recipients.
 23. Prior participation in a clinical trial of influenza A/H3N2v vaccine¹¹ or have a history of influenza A/H3N2v virus actual or potential exposure or infection prior to the first study vaccination.
¹¹And assigned to a group receiving influenza A/H3N2v vaccine, does not apply to documented placebo recipients.
 24. Occupational exposure to or substantial direct physical contact¹² with birds in the past year or during the 28 days after each study vaccination.

¹²Casual contact with birds at petting zoos or county or state fairs or having pet birds does not exclude subjects from study participation.

-
25. Occupational exposure to or substantial direct physical contact¹³ with pigs in the past year or during the 28 days after each study vaccination.

¹³Casual contact with pigs at petting zoos or county or state fairs does not exclude subjects from study participation.

26. Female subjects who are breastfeeding or plan to breastfeed at any given time from the first study vaccination until 30 days after the last study vaccination.
27. Plan to travel outside the US (continental US, Hawaii, and Alaska) within 28 days after each study vaccination.
28. Blood donation or planned blood donation within 30 days before enrollment until 30 days after the last blood draw for this study.

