7.1 Screening and Enrollment Visits

7.1.1 Visit 00, Day -7, Screening, Clinic Visit, All Subjects (Window: Day -14 to Day -5 prior to first study vaccination)

Potential subjects will be screened for eligibility up to 14 days, but no less than 5 days prior to the administration of the first study vaccination. The following activities will be performed:

- Subjects will be provided with a description of this study (purpose and study procedures) and asked to read and sign the informed consent form. The informed consent form will be signed prior to performing any study procedures, including any screening procedures.
- Demographic information will be obtained by interview of subjects.
- Eligibility criteria will be reviewed with subjects.
- Complete medical history will be obtained by interview of subjects to ensure eligibility.
- All concomitant medications taken within 60 days prior to signing the informed consent form will be reviewed with subjects. Medications reported in the eCRF are limited to those taken within 30 days prior to the first study vaccination.
- Subject receipt of licensed seasonal influenza vaccines over the previous two seasons, what type (inactivated or live attenuated), and approximate date of vaccination will be recorded on the appropriate data collection form, if known. Prior receipt of licensed seasonal influenza vaccine is not exclusionary, as long as it has been administered within the allowable window (see Section 5.1.2).
- Vital signs, including oral temperature, pulse, and blood pressure, will be obtained to ensure eligibility. Subjects must not eat or drink anything hot or cold, or smoke within 10 minutes prior to taking oral temperature.
- A targeted physical examination, including an assessment for signs suggestive of a potentially immune-mediated medical condition, may be performed, if indicated based on

review of complete medical history, by a study clinician licensed to make medical diagnoses and listed on the Form FDA 1572 as the site principal investigator or sub-investigator.

- A urine or serum pregnancy test will be performed on all women of childbearing potential and must be negative to ensure eligibility.
- Approximately 4 mL of venous blood will be collected for ESR, and performed locally by the site. The ESR value must be confirmed as less than 30 mm per hour prior to randomization and first study vaccination. The ESR, if initially elevated, may be repeated once to determine eligibility.

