- Approximately 90 mL of venous blood will be collected for baseline cytokine and chemokine levels and systems biology studies.
- Approximately 20 mL of urine will be collected for future research.

7.1.2 Visit 01, Day 1, Enrollment and First Study Vaccination (Dose 1), Clinic Visit, All Subjects

- Subject's willingness to participate will be reconfirmed and documented in the subject's study records prior to performing any further study procedures, including administration of the first study vaccination.
- Eligibility criteria, including results of the ESR evaluation, will be reviewed with subjects prior to the first study vaccination to ensure continued eligibility.
- Complete medical history and any updates obtained by interview of subjects since the screening visit will be reviewed with subjects prior to the first study vaccination to ensure continued eligibility.
- All concomitant medications will be reviewed with subjects prior to the first study vaccination for accuracy and completeness. Any new concomitant medications taken since the screening visit will be reviewed with subjects and assessed for continued eligibility prior to the first study vaccination. Medications reported in the eCRF are limited to those taken within 30 days prior to the first study vaccination.
- Vital signs, including oral temperature, pulse, and blood pressure, will be obtained prior to the first study vaccination. Vital signs assessed on Day 1 prior to the first study

vaccination will be considered as baseline. Subjects must not eat or drink anything hot or cold, or smoke within 10 minutes prior to taking oral temperature.

- Height and weight will be collected prior to the first study vaccination for the calculation of Body Mass Index (BMI).
- A targeted physical examination, including an assessment for signs suggestive of a potentially immune-mediated medical condition, may be performed prior to the first study vaccination, if indicated based on review of complete medical history and any updates obtained by interview of subjects since the screening visit, by a study clinician licensed to make medical diagnoses and listed on the Form FDA 1572 as the site principal investigator or sub-investigator.
- A urine or serum pregnancy test will be performed within 24 hours prior to the first study vaccination on all women of childbearing potential. Results must be negative and known prior to randomization and first study vaccination.

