9.1.4. Pre-Vaccination Transcriptomics Activity

The two pre-first vaccination time point RNA-Seq samples (Day -7 to -1 and Day 1) measure the baseline transcriptomics activity for each subject enrolled in this study. For each subject, baseline transcriptomic activity will be represented by averaging results for the two pre-first vaccination samples by using the sum of the read counts for each gene followed by TMM normalization as described in Section 9.1.2. Globally outlying Day -7 to -1 or Day 1 RNA-Seq samples will be excluded (see Section 9.1.3). The combined pre-first vaccination sample will be used as a reference to assess transcriptomics responses at Days 2, 4, 8, or 29 post-first vaccination. The Day 29 time point RNA-Seq sample also measures the pre-second vaccination transcriptomics activity for each subject enrolled in this study. This sample will be used as a reference to assess post-second vaccination responses (Days 2, 4, and 8 post-second vaccination) for subjects that received a second vaccine dose (Study Arms 2 and 3).

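### The 14-day inactivated-vaccine washout is counted from dose 1, not from the Visit 00 baseline draw, so a recent seasonal influenza vaccine can enter the reference for the post-dose-1 gene and cytokine responses

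*Protocol*

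**What the plan says.** **Washout.** Exclusion 18 (Protocol 5.1.2, repeated in SAP 4.3) excludes a subject who "Received licensed inactivated vaccine within 14 days prior to the first study vaccination". The per-protocol rule on non-study inactivated vaccine (Protocol 11.5.5, SAP 6.3.3) uses the same 14 days and also counts from study vaccination.

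**First baseline draw.** Under Protocol 7.1.1 subjects are "screened for eligibility up to 14 days, but no less than 5 days prior to the administration of the first study vaccination". At that same visit, "Approximately 90 mL of venous blood will be collected for baseline cytokine and chemokine levels and systems biology studies".

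**Seasonal vaccine.** Protocol 7.1.1 also states: "Prior receipt of licensed seasonal influenza vaccine is not exclusionary, as long as it has been administered within the allowable window". Receipt over the previous two seasons, the vaccine type and a rough date are recorded where known.

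**Use of the sample.** SAP 9.1.4 says "baseline transcriptomic activity will be represented by averaging results for the two pre-first vaccination samples", which it does by summing read counts gene by gene. That pooled sample is the reference for Days 2, 4, 8 and 29. Day 29 is the reference for Days 30, 32 and 36. SAP 8.2 takes the mean of the same two visits for cytokines and chemokines.

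**Safeguards.** SAP 9.1.4 drops a baseline RNA-Seq sample only if it is a global outlier. SAP 8.2 has no equivalent for cytokines. The -Omics population (SAP 6.3.4) has no exclusion for non-study vaccines.

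**The concern.** The trial takes two pre-vaccination samples to fix each subject's resting state. The washout protects the second of them (Day 1) but not the first, because its clock starts at dose 1. A subject who received a seasonal influenza vaccine shortly before screening can satisfy every rule and still give a Visit 00 sample that carries a response to that vaccine. No deviation has occurred, so neither the per-protocol nor the -Omics definition removes the sample.

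At stake is the reference for the post-dose-1 responses. In the A/H7N9 arms this covers Days 2, 4 and 29, which are three of the six time points of primary endpoint 3. In the A/H3N2v arm it covers Days 2, 4 and 8 (secondary endpoint 3). The corresponding cytokine fold changes are affected in the same way. A reference that already contains an influenza-vaccine response pulls real responses towards no change. With 10 subjects per arm, an uneven split of affected subjects would also shift the between-arm contrasts of SAP 9.2.3.

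**Working it through.** The plan states no figure on this point, so there is nothing to reproduce first.

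**1. Shortest interval from outside vaccine to Visit 00 draw**

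Inputs: the latest clearly allowed inactivated vaccine is 15 days before dose 1 (exclusion 18). The draw is 14 to 5 days before dose 1 (Protocol 7.1.1: "Window: Day -14 to Day -5 prior to first study vaccination").

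Shortest gap = 15 − (days from draw to dose 1).

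| Draw, days before dose 1 | 14 | 12 | 10 | 7 (nominal) | 5 |
|---|---|---|---|---|---|
| Shortest gap, days | 1 | 3 | 5 | 8 | 10 |

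- If receipt exactly 14 days before dose 1 is read as allowed, the range is 0 to 9 days.
- These are minimum gaps; longer ones are also allowed.
- The Day 1 sample is always at least 15 days after a clearly allowed inactivated vaccine.
- For live vaccines the 30-day rule gives 31 − 14 = 17 to 31 − 5 = 26 days, so only the inactivated-vaccine rule leaves a gap under 14 days.
- SAP 8.2 and 9.1.4 label the first baseline Day -7 to -1. Read literally against the protocol window, only draws 7 to 5 days before dose 1 qualify, and the shortest gaps are 8 to 10 days. The range narrows but the problem remains.

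**2. Effect on one subject**

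Assumptions, not in the documents: the outside vaccine raised a gene k-fold at Visit 00, the Day 1 level is normal, and the two summed samples have equal sequencing depth.

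Pooled reference = (k + 1)/2 times the true baseline, so the subject's log2 fold change falls by log2((k + 1)/2).

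- k = 2: log2(1.5) = 0.585
- k = 3: log2(2) = 1.000

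**3. Effect on an arm of 10**

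The arm mean log2 fold change is used here as an approximation to the model estimate in SAP 9.2.1. With m affected subjects the loss is m × log2((k + 1)/2)/10.

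| Affected of 10 | Loss, k = 2 | Loss, k = 3 |
|---|---|---|
| 1 | 0.058 | 0.100 |
| 2 | 0.117 | 0.200 |
| 3 | 0.175 | 0.300 |

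**4. Against the 1.5-fold cut-off**

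- True 2-fold gene, k = 2: one affected subject gives 2^(1 − 0.058) ≈ 1.92, and two give 2^(1 − 0.117) ≈ 1.84.
- To fall below 1.5 the loss must exceed 1 − 0.585 = 0.415. Since 0.415/0.0585 = 7.1, this takes 8 of 10 subjects.
- True 3-fold gene, k = 3: even 10 of 10 gives 3/2 = 1.5, which still meets the cut-off.
- With one affected subject, the genes that can cross are those truly between 1.5 and 1.5 × 2^0.058 ≈ 1.56 (k = 2), or 1.5 × 2^0.100 ≈ 1.61 (k = 3).

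**5. Between-arm contrast**

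If two affected subjects fall in one arm and none in the other, the contrast shifts by 0.117 (k = 2) to 0.200 (k = 3) on the log2 scale.

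**The case against.** The strongest reply is that the consequence is small and its frequency unknown. The documents give no enrolment calendar and no count of recently vaccinated subjects. They also do not say how long a seasonal-vaccine signature lasts. Gaps of 1 to 3 days arise only if screening is 14 to 12 days before dose 1 and the outside vaccine came 15 to 17 days before it; at the nominal visit the shortest gap is 8 days. Pooling two samples already dilutes the contamination, and the study describes itself as exploratory. All of this stands, and it limits the weight of the point. It does not close the gap in the rule.

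A reader might go further in four ways that the documents do not support.

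- **That one affected subject makes a 2-fold gene miss the cut-off.** In that subject alone the gene reads 2/1.5 = 1.33. But SAP 9.2 applies the 1.5-fold criterion to the arm-level model estimate, which stays near 1.92.
- **That all of primary endpoint 3 is affected, or that a Day 8 response is masked in the A/H7N9 arms.** Days 30, 32 and 36 use Day 29 as reference, and these arms have no omics sample at Day 8 after dose 1.
- **That exclusion 1 on acute illness creates an equal problem,** because its 72 hours also run back from vaccination. Visit 00 includes an eligibility review, a temperature check and an ESR limit, and exclusion 2 lets the investigator exclude a condition that could disturb the evaluation of responses. The documents also show no field for illness in the 72 hours before Visit 00.
- **That the proteomics baseline is equally exposed.** Its detailed methods are in a SAP addendum that is not part of these documents.

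**Conclusion.** The gap in the text is real: the washout and the first baseline draw run on different clocks, and no analysis rule catches a Visit 00 sample taken soon after an allowed inactivated vaccine. What follows is possible contamination of the post-dose-1 reference, not a shown bias.

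The size is modest: about 0.06 to 0.10 lower arm mean log2 fold change per affected subject of 10. This rests on an assumed 2- to 3-fold rise at Visit 00, equal depth, and the arm mean standing in for the model estimate. At risk are mainly genes close to the 1.5-fold cut-off, and the between-arm contrasts if affected subjects are unevenly split. Loss through added variance at the FDR step is also possible but is not quantified here. The point is worth making because the remedy is cheap, not because the endpoint is shown to be compromised.

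**What to change.** Add one rule to SAP 9.1.4 and 8.2 before analysis: if a licensed vaccine was received within 14 days before the Visit 00 draw, omit the Visit 00 sample and use Day 1 alone as that subject's pre-first-vaccination reference. Report the pooled-baseline result as a sensitivity analysis. State how approximate vaccine dates are handled, for example by using Day 1 alone when the recorded date cannot rule out receipt in that interval. Apply the same rule to proteomics only if the addendum uses the same pooled baseline.

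Reconcile the SAP's Day -7 to -1 label for the first baseline with the protocol window of Day -14 to Day -5.

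Cost: no new data collection. Seasonal vaccine history is taken at Visit 00, and Protocol 6.6 has all vaccines recorded. The earliest relevant receipt is 14 + 14 = 28 days before dose 1, inside the 30-day eCRF look-back for medications. Affected subjects have one baseline sample instead of two, so their reference is slightly noisier. Some will be misclassified because dates are approximate. If no subject is affected, the results do not change.
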